6. Have chronic liver disease, ie, AST or ALT greater than 2 times the upper limit of normal. Subjects with hepatitis B and C who have normal liver function may be enrolled.
7. Have a current malignancy (such as Hodgkin's lymphoma, B or T cell lymphoma, or myeloma) or blood cell dyscrasia (eg, polycythemia or myelofibrosis) that would lead to systemic chronic pruritus.
8. Subjects with untreated hyperthyroidism.
9. Have pruritus of psychogenic etiology (delusions of parasitosis, obsessive compulsive disorder and major depression) or neuropathic etiology (due to shingles, spinal cord injury or with neurologic deficit).
10. Have pruritus due to urticaria, drug allergy, or infection (such as pityriasis rosea or tinea or active human immunodeficiency virus [HIV]). Note: Subjects with HIV who have undetectable viral load, CD 4 counts >200 cells/cc, and stable retroviral therapy may enroll.
11. Have taken investigational medications within 30 days prior to Screening.
12. Are unwilling to discontinue specific pruritus medications for at least two weeks prior to initiation of study and throughout the study period (all severe CYP34A inhibitors - this

- includes **miconazole**, **delavirdine**, conivaptan, Clarithromycin, telithromycin, nefazodone, itraconazole, ketoconazole, indinavir, lopinavir, nelfinavir, **ritonavir**, saquinavir).
13. Within in the past 12 months, have expressed suicidal ideation with some intent to act.
 14. Started or changed medications, creams, or emollients including over-the-counter (OTC) preparations or bath oil treatment for relief of pruritus within 3 months prior to Screening.
 15. Have any social or medical condition (e.g. alcoholism, drug dependency, psychotic state) that, in the investigator's opinion, might interfere with the subject's ability to comply with the requirements of the protocol.

Statistical basis for the number of subjects to be enrolled:

This 14 patient clinical trial is powered only to determine large differences in the placebo (N=7) vs. 5 mg (N=14) groups. In power calculations, we assumed a mean of 8 NRS for the placebo vs. 5 NRS for the active with a SD of 3, and p-value of 0.05 (one sided).

| Two-sample t test with equal variances | | | | | |
|--|-----|------------------------|-----------|-------------------------|----------------------|
| | Obs | Mean | Std. Err. | Std. Dev. | [95% Conf. Interval] |
| x | 14 | 5 | 0.8017837 | 3 | 3.267852 6.732148 |
| y | 7 | 8 | 1.133893 | 3 | 5.225463 10.77454 |

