| Dispense study medication | | | X ^h | X | | | |
| Dispense subject diary | | X | X ^h | X | X ^g | | |
| Review/collect diary with subject | | | | X | X | X | X |
| Review and record adverse events | | | | X | X | X | X |

Note: NRS = numeric rating score.

* Includes up to 30 day washout from prohibited medications. The study medication and diary dispensation are to occur no more than 1-2 weeks after Screening Visit.

- a: all medications taken within 30 days prior to screening.
- b: for females of child-bearing potential.
- c: all subjects: hematology, serum chemistry will be measured at Screening, Month 1, and Month 2/EOT or early termination (ET).
- d: NRS recorded by subject daily, using diary, from screening visit through the end of the study; NRS is included in the Stanford EB Itch survey.
- e: the Stanford EB survey will be administered over the phone by a member of the research staff.
- f: photographs taken only if patient has signed photography consent
- g: a return envelope will be provided for the patient to return the study diary to Stanford after the follow up phone call

| | Schedule of Events for Phase 2 Serlopitant | | | | | | |
|--|--|---------|------------------|---------|---------|------------|------------|
| | Screening period | | Treatment period | | | Follow up | |
| | Phone call | Visit 1 | | Visit 2 | Visit 3 | Phone call | Early Term |

h: Patient letter of enrollment and study medication will be mailed to patient after determination of eligibility following the Screening Visit

Each subject will be un-blinded individually after completing 3 months of study period. All patients who complete the study will be offered a 2-month trial on active drug. Patient who received active drug in the first phase will be contacted and asked if they would like to continue on active drug for an additional 2 months. Patients who received placebo in the first phase will be contacted and asked if they would like to repeat the study on open label for 2 months.

When this occurs, the schedule of events will be as follows:

Patients who would like to continue with the treatment for the open-label extension portion of the study will be provided with the research medication and research daily diary. They will be followed up by phone at baseline, 1 month, 2 months, and 3 months (wash out). In addition, they will go to an external lab near their home for lab monitoring that will occur once a month for the two months they are on active drug.

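### Exclusions 10 and 12 leave the eligibility of an HIV subject on a listed antiretroviral ambiguous, and one reading lets such a subject enter by stopping HIV therapy

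*Combined protocol and SAP*

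**What the plan says.** Three places in the combined protocol and SAP bear on this.

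- **Exclusion criterion 10** removes people whose itch comes from urticaria, drug allergy or infection, including active HIV. Its note then makes an allowance: "Subjects with HIV who have undetectable viral load, CD 4 counts >200 cells/cc, and stable retroviral therapy may enroll". No antiretroviral regimen is excepted.
- **Exclusion criterion 12** removes people who "Are unwilling to discontinue specific pruritus medications for at least two weeks prior to initiation of study and throughout the study period". A parenthesis gives the scope as "all severe CYP34A inhibitors - this" followed by a list of named drugs, among them "indinavir, lopinavir, nelfinavir". It has no HIV exception and does not refer to exclusion 10.
- **The Schedule of Events**, in its starred footnote to the Visit 1 window, says that the window "Includes up to 30 day washout from prohibited medications". This too has no exception.

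**The concern.** Exclusion 12 tests willingness to stop a drug, not current use of it. A subject who takes a listed drug and agrees to stop is therefore not excluded by it. For an itch remedy that is an ordinary washout rule. The list, however, contains drugs taken for HIV, and exclusion 10 expressly contemplates subjects whose HIV is controlled on stable therapy. The text does not tell a site what to do when the same person falls under both provisions.

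What is at stake is subject safety and uniform screening. On one reading, a subject with suppressed HIV would interrupt antiviral treatment to join a placebo-controlled itch trial. The sample size and the analysis are not affected.

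**Working it through.** The plan states no figure on this point. The check is a count, a comparison of the texts, and a sum of days.

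**1. Count of the list in exclusion 12.** The named drugs are miconazole, delavirdine, conivaptan, clarithromycin, telithromycin, nefazodone, itraconazole, ketoconazole, indinavir, lopinavir, nelfinavir, ritonavir and saquinavir: 13 in all. Delavirdine, indinavir, lopinavir, nelfinavir, ritonavir and saquinavir are antiretrovirals: 6 of 13. That classification is general drug-class knowledge. These six are not itch treatments, so the criterion's opening words and its list do not match.

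**2. An HIV subject who meets the exclusion 10 note and takes one of the six.**

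| Reading of exclusion 12 | Result for this subject |
|---|---|
| Limited to drugs taken for pruritus | The drug is outside the rule; it continues and the subject may enroll |
| Covers every listed drug; subject will not stop | Excluded by exclusion 12 |
| Covers every listed drug; subject agrees to stop | Not excluded by exclusion 12; whether exclusion 10 still holds depends on when it is judged |

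**3. When the criteria are judged.** In the Schedule of Events, the inclusion/exclusion row is marked at the screening call and at Visit 1 only. The later eligibility column marks review of the medical history, pregnancy test and laboratory results, but does not mark the criteria again. A subject could thus satisfy exclusion 10 on stable therapy at screening and then stop under exclusion 12. The scheduled blood tests are hematology and serum chemistry; viral load and CD4 count are not listed, so the schedule itself would not show a later loss of the exclusion 10 conditions.

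**4. Time off drug on the third reading.** Inputs: at least 14 days before the start (exclusion 12), or up to 30 days (washout footnote); Day 60 for end of treatment and Day 90 for the Month 3 call (Schedule of Events). The start is taken as Day 0.

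Nominal days off drug = washout days + last day covered.

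| | To end of treatment (Day 60) | To Month 3 (Day 90) |
|---|---|---|
| 14-day washout | 14 + 60 = 74 | 14 + 90 = 104 |
| 30-day washout | 30 + 60 = 90 | 30 + 90 = 120 |

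Each end day has a window of ±14 days. Exclusion 12 applies "for at least two weeks prior to initiation of study and throughout the study period", and the paragraph on un-blinding counts the study period as three months, which favors the right-hand column. The 30-day row is an upper figure: the same footnote wants study medication dispensed within one to two weeks of the Screening Visit, so a 30-day washout starting at that visit would not fit.

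**The case against.** A reader might infer that exclusions 10 and 12 contradict each other, or that the protocol requires subjects with HIV to give up treatment. The documents do not support either inference. Eligibility criteria apply jointly. The note prevents controlled HIV from triggering exclusion 10 and does not waive exclusion 12. A subject on a regimen outside exclusion 12 can satisfy both, and one who will not stop a listed drug is simply excluded. Someone who has just stopped part of a regimen arguably no longer has stable therapy, so the two rules read together may point to non-enrollment. The opening words of exclusion 12 may also confine it to drugs taken for itch.

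There are general safeguards as well. Exclusion 4 lets the investigator keep out anyone at undue risk, inclusion 8 requires good health on examination, history and laboratory tests, and medications are recorded at the screening call and Visit 1.

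Most of this stands, and it rules out calling the criteria contradictory. It does not settle the wording. The argument from lost stability works only if exclusion 10 is judged again after the washout, which the schedule does not mark. The narrower reading of exclusion 12 is possible, but its own list tells against it. Exclusion 4 depends on individual judgment and does not say how exclusions 10 and 12 fit together.

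**Conclusion.** The point holds as a low-impact safety wording defect. For an HIV subject on one of the 6 listed antiretrovirals, or on another drug in the class that exclusion 12 describes, the text supports three different outcomes. One is entry after stopping HIV therapy for about 74 to 104 nominal days, or 90 to 120 with a 30-day washout.

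This rests on the general classification of the six drugs and on Day 0 as the start of the study. The documents give no number of subjects likely to be affected. In a trial described as 14 patients, with groups listed as 7 and 14, it may be zero. Nothing in the documents shows that such a subject was expected to stop treatment, only that the wording does not prevent it.

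**What to change.** Reconcile exclusion 10, exclusion 12 and the washout footnote so that a subject on a listed antiretroviral has one unambiguous eligibility status and no reading makes stopping HIV therapy a route to entry. In the same edit, resolve the mismatch in exclusion 12 between its reference to pruritus medications and its enzyme-inhibitor list. Which status applies is a clinical choice for the sponsor.

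The cost is about one sentence of text. A rare subject's eligibility status might change; the sample size and the analysis do not.

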There is a trend towards greater reduction in itch severity as measured by daily self-reported NRS itch severity for serlopitant 5 mg as compared to placebo during the two month active trial period, though this was not statistically significant.

8) Experimental design and data analysis:

Inclusion criteria:

1. Males or females who are at least 13 years of age.
2. Willing and able to understand and sign informed assent/consent. Adolescents will need a parent or guardian willing and able to give consent.
3. Clinical diagnosis of epidermolysis bullosa (DEB, EBS, or JEB).
4. Subjects must have pruritus of at least 6 weeks duration
5. History of chronic pruritus
6. On the Stanford EB Itch survey, subject must have a Screening Visit (Visit 1) NRS pruritus score of at least 4 on either (1) average itch score in the past 24 hours or (2) bathing/dressing itch score in the past 24 hours.
7. Female subjects must be of non-childbearing potential (ie, post-menopausal for at least 1 year, had a hysterectomy, or had a tubal ligation) or, if of childbearing potential, must have a confirmed negative urine pregnancy test prior to study treatment and be willing to use effective contraception for the duration of the trial. Effective contraception is defined as follows: oral/implant/injectable/ transdermal contraceptives, intrauterine device, condom with spermicide, or diaphragm with spermicide. Abstinence or partner's vasectomy is acceptable if the female agrees to use effective contraception if she decides to discontinue abstinence or to have sexual intercourse with a non-vasectomized partner.
8. Judged to be in good health based upon the results of a physical examination, medical history, and safety laboratory tests.

Exclusion criteria:

1. Have any medical condition or disability that would interfere with the assessment of safety or efficacy in this trial or would compromise the ability of the subject to travel to Stanford or to undergo study procedures or to give informed consent.
2. Have a history of sensitivity to any components of the study material.
3. Are females of childbearing potential who are unwilling to use adequate contraception or who are breast feeding.
4. Have any chronic or acute medical condition that, in the opinion of the investigator, might interfere with the study results or place the subject at undue risk.
5. Have chronic renal disease, ie, serum creatinine greater than 2 times the upper limit of normal.

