| combined | 21 | 6 | 0.7121396 | 3.263434 | 4.514503 7.485497 |
| diff | -3 | 1.38873 | | -5.906646 | -0.0933544 |
| Diff= mean (x) – mean (y) | | | | t = -2.1602 | |
| Ho: diff = 0 | | | | Degrees of freedom = 19 | |
| Ha: diff < 0 | | Ha: diff != 0 | | Ha: diff > 0 | |
| Pr(T < t) = 0.0219 | | Pr(T > t) = 0.0437 | | Pr(T > t) = 0.9781 | |

Statistical plan for analyzing at least the primary hypothesis:

The sample size is powered to detect small differences in NRS score. Because itch is subjective and varies daily, subjects will be asked to keep an itch diary every day. For each subject, we will plot their average itch scores over time before and after drug intervention. For each dosage group, we will use linear regression methods with mix effects (GLM, SAS) to track the change in itch in each of the groups from baseline. This study will provide the effect size, standard deviation and range of itch scores in EB patients in order to properly power a larger phase 2 trial. This study can detect large differences in itch scores should Serlopitant decrease itch from severe to low-none at 1 and 2 months. At the 3 month follow up, we will measure the durability and length of response.

Matrix showing procedure plan for each study visit:

| Schedule of Events for Phase 2 Serlopitant | | | | | | | |
|--|------------------|-----------------|------------------------------|----------------|----------------|----------------|----------------|
| | Screening period | | Treatment period | | | Follow up | |
| | Phone call | Visit 1 | | Visit 2 | Visit 3 | Phone call | Early Term |
| | Screening call | Screening visit | Determination of Eligibility | Month 1 | Month 2/EOT | Month 3 | |
| Examination | Day -60 to -30 | Day -44* to -1 | Months 6 to 0 | Day 30 ±14 | Day 60 ±14 | Day 90 ±14 | |
| Informed consent/ Photographic consent | | X | | | | | |
| Demographics | | X | | | | | |
| Medical history | | X | Review | | | | |
| Prior ^a & current medications | X | X | | X | X | X | X |
| Abbreviated physical examination | | X | | | X | | X |
| Vital signs | | X | | X | X | | X |
| Urine pregnancy test (UPT) ^b | | X | Review results | X | X | | X |
| Inclusion/exclusion criteria | X | X | | | | | |
| Blood samples for clinical laboratory tests ^c | | X ^c | Review results | X ^c | X ^c | | X ^c |
| Randomization | | | X ^h | | | | |
| NRS ^d & Stanford EB survey | | X | | X | X | X ^e | X |
| Photograph the affected area ^f | | X | | X | X | | X |

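### The stated total of 14 patients contradicts the stated arms of 7 and 14, which sum to 21; the supporting table fits only 14 + 7, and no allocation ratio is given

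*Combined protocol and SAP*

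**What the plan says.** The planned enrolment is given in section 8 of the combined protocol and SAP, under the heading on the statistical basis for the number of subjects. The sentence reads: "This 14 patient clinical trial is powered only to determine large differences in the placebo (N=7) vs. 5 mg (N=14) groups". The next sentence supplies the inputs: "we assumed a mean of 8 NRS for the placebo vs. 5 NRS for the active", with a standard deviation of 3 and a one-sided 0.05 criterion.

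The two-sample t-test table that follows has an active row, "x | 14 | 5 | 0.8017837 | 3 | 3.267852 6.732148", a placebo row with 7 observations and mean 8, and a pooled row, "combined | 21 | 6 | 0.7121396 | 3.263434 | 4.514503 7.485497". It also prints "Degrees of freedom = 19", t = -2.1602, a one-sided p of 0.0219 and a two-sided p of 0.0437.

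No other section gives a total, and none gives an allocation ratio. Randomisation appears only as a row in the schedule of events. No power figure is stated.

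**The concern.** Total enrolment and allocation are figures the trial is run on, and this is the only place where the plan sets them. It gives 14 as the total and, in the same sentence, arms that make 21. The gap is 7 patients, one third of the larger figure.

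If 21 is right, the table describes this trial and only one number needs correcting. If 14 is right, the plan does not say how the 14 are split, and the table shows more precision than the trial would have. Section 8 also says the study is meant to supply the effect size and standard deviation for powering a larger trial, so readers need to know how many patients those estimates will rest on.

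**Working it through.** **Inputs, all from section 8:** stated total 14; placebo n = 7; 5 mg n = 14; means 8 (placebo) and 5 (active); common SD 3; one-sided alpha 0.05.

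**Step 1: the total.** 7 + 14 = 21, not 14.

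**Step 2: reproduce the printed table at 14 active + 7 placebo.**

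- Active-arm SE = 3/√14 = 0.80178. Placebo SE = 3/√7 = 1.13389. Both match.
- Combined mean = (14×5 + 7×8)/21 = 126/21 = 6. Matches.
- Combined SD = √[(13×9 + 6×9 + 14×1² + 7×2²)/20] = √(213/20) = 3.26343; SE = 3.26343/√21 = 0.71214. Both match.
- SE of the difference = 3×√(1/14 + 1/7) = 1.38873. Matches.
- t = (5 − 8)/1.38873 = −2.1602, with df = 14 + 7 − 2 = 19. Matches.
- 95% CI for the difference: −5.9066 to −0.0934; p = 0.0219 one-sided and 0.0437 two-sided. All match.

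The table is therefore correct for 14 + 7. Swapping the arms (7 active, 14 placebo) would give a combined mean of (7×5 + 14×8)/21 = 7, not the printed 6.

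**Step 3: can the table describe 14 patients?** Any two-arm split of 14 has df = 12, not 19. The SE of the difference is smallest with equal arms, where it is 3×√(2/7) = 1.6036, already above the printed 1.38873. So no split of 14 gives the printed result.

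**Step 4: what changes if the total is 14.** The splits below are assumptions; the documents give none. SE = 3×√(1/n₁ + 1/n₂). The smallest observed difference reaching one-sided 0.05 is t(0.95, df)×SE, with t = 1.7291 at df 19 and 1.7823 at df 12. Power is from the noncentral t with noncentrality 3/SE, one-sided at 0.05.

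| Active + placebo | SE | t | df | 95% CI | p, one-sided / two-sided | Smallest passing difference | One-sided power |
|---|---|---|---|---|---|---|---|
| 14 + 7 (as printed) | 1.389 | −2.160 | 19 | −5.91 to −0.09 | 0.022 / 0.044 | 2.40 | 66.9% |
| 7 + 7 | 1.604 | −1.871 | 12 | −6.49 to 0.49 | 0.043 / 0.086 | 2.86 | 54.7% |
| 9 + 5 | 1.673 | −1.793 | 12 | −6.65 to 0.65 | 0.049 / 0.098 | 2.98 | 51.8% |
| 10 + 4 | 1.775 | −1.690 | 12 | −6.87 to 0.87 | 0.058 / 0.117 | 3.16 | 48.0% |

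At the assumed difference of 3, the plan's one-sided criterion is met at 7 + 7 and 9 + 5 and missed at 10 + 4. The two-sided interval includes zero in all three 14-patient cases.

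**Step 5: which printed rows survive at 14.** The active row, the combined row and every line on the difference would change. At 7 + 7, for example, the active row becomes SE 1.134 with CI 2.23 to 7.77, and the combined mean becomes 6.5. The placebo row is unchanged only if placebo stays at 7.

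**The case against.** The strongest reply is that this is a slip in a single number. The two arm sizes, the observation counts, the combined count, the combined mean and the degrees of freedom all agree on 14 + 7, and only the total disagrees. On that reading nothing is lost and the implied ratio is plainly 2:1. This is probably right, but it does not close the point: the arm sizes and the table come from one calculation, so their agreement shows what was calculated and not how many patients the trial intends to enrol. The text would look the same if 14 were the intended enrolment set beside an unrevised table.

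A second reply is that every unfavourable figure depends on a total of 14 with a split found nowhere in the documents. That is so, and those figures are offered only as a range under stated assumptions.

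A third is that loss of two-sided significance has little weight when the plan sets a one-sided criterion, and that a p-value computed at assumed means is not a planning quantity. This stands; precision and power are the relevant measures.

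Finally, the trial is exploratory and makes no confirmatory claim from this table. That limits the consequences, but it does not excuse a planned sample size that contradicts itself.

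**Conclusion.** The concern holds and must be fixed. The stated total conflicts with the stated arms by 7 patients, the table is right for 14 active and 7 placebo and for no trial of 14, and nothing else in the document settles the total or the ratio.

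The evidence favours 21 at 2:1, in which case the error is confined to one number and the printed precision stands. If 14 is the true enrolment, the SE of the difference rises from 1.39 to between 1.60 and 1.77, and one-sided power falls from about 67% to between 48% and 55%. Those ranges assume the plan's means and SD and splits from 7 + 7 to 10 + 4.

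**What to change.** State one planned total and the allocation ratio actually used, and carry the same numbers through the sentence, the table and the randomisation list.

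- If the arms are 14 and 7, change the total to 21 and state the ratio as 2:1 active to placebo. The table stays as printed.
- If the arms are anything else, give them and rerun the table for those numbers.

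Section 7 already reports a comparison of 5 mg with placebo, "during the two month active trial period, though this was not statistically significant". The text does not say whether these data come from this trial. If they do, report the planned number and the number actually randomised separately; a planned number should not be chosen after the event.

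The cost is one sentence if the arms are 14 and 7, and otherwise also a rerun of the table. No extra patients are needed. The only drawback is that the printed standard error, interval and p-values become less favourable if the total proves to be 14.

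### The plan claims power for small NRS differences, contradicts this elsewhere and reports no power; at its own inputs a t test has 67% power for 3 points and 17% for 1

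*Combined protocol and SAP*

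**What the plan says.** All the relevant text is in section 8 of the combined protocol and SAP.

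- **Statistical basis for the number of subjects to be enrolled.** The opening sentence reads "This 14 patient clinical trial is powered only to determine large differences in the placebo (N=7) vs. 5 mg (N=14) groups". For its power calculations the plan "assumed a mean of 8 NRS for the placebo vs. 5 NRS for the active with a SD of 3", at a one-sided 0.05 level. A printed two-sample t test follows, with 14 observations at mean 5 and 7 at mean 8. Its pooled row reads "combined | 21 | 6 | 0.7121396", with t = -2.1602 on 19 degrees of freedom and a one-sided p of 0.0219.
- **Statistical plan for analyzing at least the primary hypothesis.** This opens with "The sample size is powered to detect small differences in NRS score". Later in the same paragraph it says "This study can detect large differences in itch scores should Serlopitant decrease itch from severe to low-none at 1 and 2 months". The planned analysis is different from the sizing test: "we will use linear regression methods with mix effects (GLM, SAS) to track the change in itch". The study is also meant to supply the effect size and SD "in order to properly power a larger phase 2 trial".

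Neither a target power nor an achieved power is stated anywhere.

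**The concern.** The statements about sensitivity cannot all be true. The sample-size section limits the power to large differences, so it cannot be read alongside a claim of power for small ones.

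A stated power would show which sentence is right, but there is none. The printed table answers another question: if the observed means were exactly 5 and 8 with SD 3, would the result be significant? Power is the probability of a significant result when the true difference is 3 points, and the table does not give it.

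What is at stake is how the results are read. Someone who takes the small-differences sentence at face value could treat a non-significant result as evidence against a modest effect. Because the study is meant to inform the size of a larger trial, its own sensitivity should be stated correctly. No endpoint, analysis or decision rule depends on the sentence.

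**Working it through.** **Inputs, all from the sample-size section.** Means 8 (placebo) and 5 (active), so a difference of 3; SD 3; 7 placebo and 14 active; one-sided alpha 0.05.

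**Step 1. Reproduce the printed test.**

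- SE = 3 × √(1/14 + 1/7) = 1.38873, as printed.
- t = -3 / 1.38873 = -2.1602 on 14 + 7 - 2 = 19 df, as printed.
- One-sided p = 0.0219 and two-sided p = 0.0437, as printed.

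The table is arithmetically correct, but it contains no power.

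**Step 2. Power of that test.** Power = P(T > 1.7291), where 1.7291 is the one-sided 5% critical value on 19 df and T is noncentral t on 19 df with noncentrality δ / 1.38873.

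| True difference δ (NRS points) | Noncentrality | Power | Missed |
|---|---|---|---|
| 1 | 0.720 | 17.1% | 83% |
| 2 | 1.440 | 39.9% | 60% |
| 3 (the plan's assumption) | 2.160 | 66.9% | 33% |
| 4 | 2.880 | 87.1% | 13% |
| 5 | 3.600 | 96.6% | 3% |

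Power reaches 80% at δ = 3.58 points. A simulation of 1,000,000 trials gave 66.8% for 3 points and 17.1% for 1 point.

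**Step 3. Patients needed for 80% power** (same test, SD 3, 2:1 allocation, smallest total that reaches 80%).

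| Difference | Active vs placebo | Total | Power |
|---|---|---|---|
| 3 points | 20 vs 10 | 30 | 80.9% |
| 2 points | 44 vs 22 | 66 | 81.1% |
| 1 point | 168 vs 84 | 252 | 80.0% |

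The plan states 21 or 14.

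**Step 4. If the total is 14.** The document gives no split of 14, so these are assumptions. Power for 3 points is 54.7% (7 vs 7), 54.0% (8 vs 6), 51.8% (9 vs 5) or 48.0% (10 vs 4).

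**Step 5. Can a non-significant result exclude 3 points?** This is the simulated share of non-significant trials (14 vs 7, SD 3) whose confidence interval still includes a 3-point benefit.

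| True effect | Two-sided 95% CI | 90% CI (matches the one-sided 0.05 test) |
|---|---|---|
| 0 | 44% | 30% |
| 1 | 67% | 52% |
| 2 | 83% | 72% |
| 3 | 92% | 85% |

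With either interval, a non-significant result will often leave a 3-point effect open.

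**The case against.** **The consequence is limited.** The opposite statement appears twice, the study is described as a source of planning figures, and nothing operational depends on the sentence. This is fair and limits the weight of the point. However, the sentence opens the primary analysis plan, and removing it would not supply the missing power or settle the total.

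**The planned analysis is a mixed model on daily diary scores, not a t test.** This is the strongest objection. Suppose adjustment for baseline cut the residual SD to 3 × √(1 - ρ²), where ρ is an assumed correlation that the plan does not give. Power for 3 points would then be 78% at ρ = 0.5 and 90% at ρ = 0.7, so 67% may understate the sensitivity of the final analysis. It does not rescue the claim: at ρ = 0.7 power is still only 25% for 1 point and 62% for 2. The real power of the mixed model cannot be computed, because the plan gives no SD or correlation for it.

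**Small and large are undefined.** True: 1 or 2 points for small, and 4 to 5 for large, are assumed meanings. The conclusion does not depend on them. The 3-point difference used for sizing has 67% power, and any smaller difference has less.

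**The printed calculation clearly used 21.** It did: the arm sizes, the pooled count and the 19 df all agree. What remains unclear is whether 21 or 14 patients are to be enrolled, and so which power applies to the trial.

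**Conclusion.** The concern holds. The plan contradicts itself on what the trial can detect, reports no power, and makes a claim about small differences that its own inputs do not support. For 14 vs 7, SD 3 and one-sided 0.05, a two-sample t test has 67% power for 3 points, 40% for 2 and 17% for 1, with 80% at about 3.6 points. A claim about large differences is defensible if large means 4 to 5 points (87% to 97%). If only 14 patients are enrolled, power for 3 points falls to between 48% and 55%, depending on the assumed split.

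These figures rest on the plan's SD of 3, its one-sided test and no dropout, and they describe the sizing test rather than the mixed model. The point should be fixed, but it affects interpretation only.

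**What to change.** 1. Delete the small-differences sentence from the statistical plan.
2. Reconcile the 14-patient total with 7 + 14 = 21.
3. Replace the t-test printout with a power statement for the adopted total. For 14 vs 7 it could read: *With 14 active and 7 placebo patients, SD 3 and one-sided alpha 0.05, a two-sample t test has 67% power for a 3-point difference and 80% power for 3.6 points; a non-significant result may not exclude a 3-point effect.* Recompute it if another total is adopted. It is worth adding that these figures are for the sizing t test and that power for the mixed model was not derived.

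The cost is protocol wording. The stated sensitivity becomes less favourable, but no patients are added and no analysis changes.
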